5.1.2.2 Long-term (2 y cPNA) secondary outcomes

- Survival
- Proportion of scores < 1 SD and < 2 SD below mean, for the primary cognitive sub-score outcome at 2 y cPNA
- Individual components of the Bayley-4 at approximately 2 y cPNA
- Neurobehaviour using the Infant Toddler Social-Emotional Assessment (ITSEA)⁵³
- Social communication using the Communication and Symbolic Behaviour Scales Infant-Toddler Checklist (CSBS-ITC) for early recognition of risk behaviours that may be predictive of later behavioural difficulties such as diagnosis of autism spectrum disorder
- Growth velocity
- Anthropometry including weight, height, BMI, fat-free mass
- Primary caregiver mental well-being
 - GAD-7
 - Center for Epidemiologic Studies Depression Scale Revised (CESD-R).
- 5.1.3 Circadian rhythm biological sub-study (KEMH only, n=~70): confirming intervention effect on rhythms
 - Time to onset, mesor, amplitude, and acrophase of circadian rhythms in temperature, heart rate, oxygen saturation, salivary melatonin and cortisol and/or urinary melatonin, and buccal cell clock gene expression at study entry, 7 d, 14 d, 28 d and then 4 weekly until discharge home.
- 5.1.4 Social Communication sub-study (n=infants identified at risk of ASD using the CSBS-ITC, in centres where ADOS-2 testing is available)
 - Assessment at 2 years corrected postnatal age with The Toddler Module of the Autism Diagnostic Observation Schedule - Second Edition (ADOS-2)⁵⁴. Two outcomes will be reported from the ADOS-2.
 - the continuous scores of the ADOS-2 (i.e., autism behavioural severity)
 - the dichotomous outcome of whether or not children exceed the 'ASD' threshold (to be defined).
- 5.1.5 Neonatal lung function and body composition sub-study (KEMH only, n=128)
 - Tidal volume
 - Respiratory rate
 - Area under the flow volume curve
 - Body volume
 - Body fat and fat free mass, and % body fat

5.1.6 Measurement of infant sleep quality and duration sub-study

- Parents will be asked to complete the Brief Infant Sleep Questionnaire (BISQ-R; 33 items) at 2 months and 6 months corrected postnatal age, to provide detail on their infants sleep behaviours over the previous 2 weeks.
- Parents will also be asked to keep a sleep diary of their own sleep behaviours over the same interval.

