- Infants and parents recruited to the sleep sub-study from KEMH or from Fiona Stanley Hospital (FSH), will also be invited to participate in physiological studies to measure how the cycled light and noise intervention influences sleep during hospitalisation (phase 1) and after discharge (phase 2).
 - Phase 1 (Completed December 2021): sleep and wakefulness will be measured using actigraphy at baseline, 7 d, 14 d, 28 d, and then every 4 weeks until 36 w postmenstrual age in infants recruited from KEMH.
 - Phase 2: sleep and wakefulness will be measured in both the infant and the main caregiver (parent) using actigraphy at 36 w postmenstrual age (or prior to discharge home, whichever comes first), at 2 months corrected postnatal age and at 6 months corrected postnatal age. Saliva swabs will also be obtained from the infants before they go to sleep at night, and again when they wake in the morning, at each of these times.

Key reported measures will include:

- Total sleep time
- Total day (6AM-8PM) and night (8PM-6AM) sleep
- Sleep/activity ratio
- Number of sleep awakenings after sleep onset
- Longest continuous sleep during daytime and night-time
- Peak salivary melatonin
- Day:night salivary melatonin ratio

5.1.7 Magnetic Resonance Imaging sub-study

MRI outcomes will include a calculation of a global abnormality score, derived from metrics obtained from T1- and T2-weighted images. Two different scoring systems will be applied to the conventional sequences.^{55,56}

Other MR measures of cerebral integrity will be derived from diffusion weighted imaging and include: Fractional anisotropy apparent diffusion coefficient in multiple areas of the brain.

An analysis of 208 MR images (n=104 from each group) will identify differences in the primary outcome of MRI Global Brain Abnormality Score (GBAS) of 2.85 assuming a standard deviation of 5 and adjusting for missing subjects (10 %) and 30 % multiple births.

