5.3 Minimisation of Bias

Infants meeting study eligibility criteria will be randomised to a control environment or a cycled environment (light and noise) from birth until discharge. Randomisation will use variable block sizes (block size 4 to 6) stratified by both gestation (<28 w, 28⁰-31⁶ w PMA) and study site, using the concealed randomisation facility built into the REDCap database via computer generated, randomisation tables developed and uploaded by the trial biostatistician ([name]) and maintained by the Trial Management Team at the Telethon Kids Institute. Randomisation will maintain equal group sizes between the two study arms. Infants from multiple pregnancies will be assigned to the same group, to ensure planned secondary analyses on parent mental well-being and attachment are not confounded by conflicting infant circadian rhythms.

Blinding of families, healthcare providers during initial hospitalisation, and the co-ordinating study investigators to group allocation is not possible for this intervention. However, outcome assessors and data analysts will be blinded to allocation.

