10.2 Sample Size, Study Power, and Significance

A sample size of 954 is required to detect a difference of at least 4 points on the cognitive sub-score at 2 years corrected postnatal age.

This calculated sample size assumes 90 % power, 5 % significance level to detect a mean difference of 4 points in the primary outcome for a known population standard deviation of 15 points, with a 2-sided t-test, 10 % loss to follow-up, and 30 % adjustment for multiple births.

- A 2 sample t-test for mean difference of 4 points with SD of 15 points = 297 subjects/group resulting in a total unadjusted sample size of 594.
- The unadjusted sample size was rounded up to 600, then adjusted for expected 30 % prevalence of multiple births in the recruited population, and a 10 % loss to follow-up for the long-term outcome. 600/0.7/0.9 = 952.3 subjects
- The final sample size was rounded to 954, to ensure an even allocation of subjects to the two study groups.

A blinded interim analysis will be performed after 25 % and 50 % of participants have reached the 2 year endpoint to assess the assumptions in the sample size calculation.

Sample sizes for sub-studies target 80 % power to detect 0.5 SD mean difference with significance at the 5 % level.

Circadian rhythmicity will be assessed using cosinor analysis (non-linear regression) to determine mesor, amplitude, and acrophase of rhythms.

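### The lung-function and body-composition sub-study size (5.1.5, n=128) has no allowance for co-randomised multiples, so it falls somewhat short of the 80% power for 0.5 SD given in 10.2

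*Protocol*

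**What the plan says.** Section 5.1.5 gives the size of this single-site sub-study in its title only: "Neonatal lung function and body composition sub-study (KEMH only, n=128". It shows no derivation and does not mention siblings or missing measurements. The general statement is in 10.2: "Sample sizes for sub-studies target 80 % power to detect 0.5 SD mean difference with significance at the 5 % level".

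Three other places bear on it.

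- **Allocation (5.3).** "Infants from multiple pregnancies will be assigned to the same group".
- **Main trial (10.2).** The unadjusted total is rounded to 600 and then "adjusted for expected 30 % prevalence of multiple births in the recruited population, and a 10 % loss to follow-up for the long-term outcome", by dividing by 0.7 and by 0.9.
- **MRI sub-study (5.1.7).** The size of 208 is stated as "adjusting for missing subjects (10 %) and 30 % multiple births".

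Neither 5.1.5 nor 7.1.9 and 7.1.10, which describe the measurements, limits the sub-study to singletons or to one infant per family.

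**The concern.** A size of 64 per arm gives 80% power for 0.5 SD only if the 128 infants are statistically independent and every one is measured. The trial's own allocation rule breaks the first condition: twins are in the same arm and tend to resemble each other in body size and breathing, so a pair carries less information than two unrelated infants. The protocol recognises this for the main trial and for the MRI sub-study but not here, while one sentence in 10.2 covers the sub-studies in general.

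What is at stake is how the sub-study will be read. If the report repeats 80% power for 0.5 SD, a null result on tidal volume or fat-free mass will appear to exclude that effect more firmly than the design allows.

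**Working it through.** **Inputs from the protocol.** Total 128 (5.1.5); 80% power, 0.5 SD and 5% level (10.2); equal arms (5.3); siblings in the same arm (5.3); 30% multiples and 10% loss (10.2). The two-sided t-test is stated for the main trial only and is taken over here. A one-sided test would need about 51 per arm, or 102 in all, so only the two-sided test fits 128.

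**Assumed inputs.** The ICC between siblings (0.3, 0.5, 0.8); all multiples are twins, with both enrolled; the 30% is a share of infants; and, in step 4, 10% unmeasured.

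**Step 1: reproduce 128.** For a two-sided two-sample t-test with d = 0.5, alpha = 0.05 and power 0.80, n per arm = 63.8, rounded up to 64, so N = 2 x 64 = 128. Power at 64 per arm is 80.1%. The figure is therefore the uninflated one.

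**Step 2: check that the other sizes are inflated.**
- Main trial: 4/15 SD at 90% power needs 296.5, so 297 per arm and 594 in all, rounded to 600. Then 600/0.7/0.9 = 952.4, taken to 954.
- MRI: 2.85/5 = 0.57 SD at 90% power needs 65.66 per arm. Then 2 x 65.66/(0.7 x 0.9) = 208.4, against the stated 208.

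Both carry the allowance; 128 does not.

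**Step 3: clustering only, all 128 measured.** With a share p of infants in twin pairs, the design effect is 1 + p x ICC = 1 + 0.3 x ICC. Effective n per arm = 64/(1 + 0.3 x ICC).

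| ICC | Design effect | Effective n per arm | Power for 0.5 SD | Detectable at 80% |
|---|---|---|---|---|
| 0.3 | 1.09 | 58.7 | 77% | 0.52 SD |
| 0.5 | 1.15 | 55.7 | 74% | 0.54 SD |
| 0.8 | 1.24 | 51.6 | 71% | 0.56 SD |

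**Step 4: clustering and 10% unmeasured.** Effective n per arm = 64 x 0.9/(1 + 0.3 x ICC).

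| ICC | Effective n per arm | Power for 0.5 SD | Detectable at 80% |
|---|---|---|---|
| 0.3 | 52.8 | 72% | 0.55 SD |
| 0.5 | 50.1 | 70% | 0.57 SD |
| 0.8 | 46.5 | 66% | 0.59 SD |

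**Step 5: the protocol's own rule as a lower bound.** 64 x 0.7 x 0.9 = 40.3 per arm gives 60% power and a detectable difference of 0.63 SD. With the 0.7 factor alone, 64 x 0.7 = 44.8 per arm gives 65%. Multiplying by 0.7 in effect discards every infant from a multiple birth, which is harsher than any ICC up to 1 would justify under the twin model.

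**The case against.** **The missing-data part is weakly supported.** In 10.2 the 10% is tied to the long-term outcome, whereas lung function and the neonatal body-composition measurement take place at 36 weeks, and 7.1.9 describes the breathing tests as minimally invasive and usually possible without disturbing sleep. The protocol also does not say whether 128 counts infants enrolled or measured; if measured, this part disappears. That stands, and it is why step 4 is separate and conditional. Two things keep it from being dropped: the MRI sub-study applies 10% to a scan near term, and 7.1.10 also schedules fat-free mass at 2 years, where the 10% loss applies directly.

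**The ICC is not in the documents, and both twins need not be enrolled.** Also correct. Enrolling one sibling per family would reduce the design effect. The direction does not depend on the value, however: 80.1% leaves no room, and any positive ICC among enrolled siblings takes power below 80%.

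**10.2 speaks of a target and is generic.** Its link to 128 is inferred from an exact numerical match. It does not describe every sub-study either: MRI is sized for 0.57 SD, and the circadian sub-study has its own longitudinal calculation in 6.1. This softens the wording of the point, but this sub-study has no other stated basis for its size.

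**Covariate adjustment could recover the loss.** At ICC 0.5 with all infants measured, covariates explaining 1 - 1/1.15 = 13% of the variance would restore 64 effective infants per arm. That is possible, but the protocol claims no such gain for this sub-study.

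**Stronger readings.** A reader might infer from the main-trial rule that power is really 60%, or that 128/0.7/0.9 = 203.2, so about 204 infants, are required. The documents do not support either as an estimate: the rule is conservative and its 10% was set for 2 years. Nor do they support a single figure such as 70%, which fixes an ICC and a missing rate that the protocol never gives.

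**Conclusion.** The point holds as an inconsistency in the stated power; no printed calculation is wrong. The size of 128 is the uninflated t-test number, in a trial that assigns siblings together and allows for this in the other two sizes reproduced here. The firm part is the clustering shortfall: about 71% to 77% power instead of 80%, or a detectable difference of about 0.52 to 0.56 SD, for ICC 0.3 to 0.8 with twins both enrolled and all 128 measured. If 10% are also unmeasured, the figures are about 66% to 72% and 0.55 to 0.59 SD. The 60% and 0.63 SD from the protocol's own rule serve only as a conservative lower bound.

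The issue is confined to one single-site sub-study and does not touch the primary endpoint. It should be corrected because the remedy is cheap and the present wording is too favourable.

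**What to change.** Keep n=128 and change the text.

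1. In 5.1.5, say whether 128 means infants enrolled or infants with a measurement, and whether both siblings of a multiple birth may be included.
2. In 5.1.5 or 10.2, restate the power for 0.5 SD, or the difference detectable with 80% power, as a range with the assumed ICC and missing rate beside it. For example: 71% to 77% with all measured and ICC 0.3 to 0.8; 66% to 72% with 10% unmeasured.
3. Qualify the general sentence in 10.2 so that it does not claim 80% power at 0.5 SD for this sub-study.
4. Include the multiple-birth identifier in the sub-study analysis, as the mixed model in 10.1 already does for the primary outcome.

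The cost is wording only. No participants are added, and the stated power becomes less favourable.

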5.1.8 Infection and Immunology sub-study

- Primary outcome will be hospitalisations for bacterial or viral infection in the first two years of life.
- Secondary outcomes will include:
 - Number of febrile episodes (> $38.5 \,^{\circ}$ C) in the first 2 years of life
 - Number of courses of antibiotics
 - Number of hospitalisations for respiratory and/or gastrointestinal illnesses.
 - Number of respiratory viral infections
 - Doctor diagnosis of asthma or wheezy illness
 - Number of gastrointestinal viral infections
 - Indices of neutrophil and immune function
 - o Indices of airway epithelial cell function

5.1.9 Health economic outcomes

Economic outcomes will be assessed at neonatal discharge and at 2 years cPNA, and will include estimation of long-term outcomes:

Given the low cost of the intervention and anticipated fewer days in the NICU (~\$2 000-\$3 000/d) for the intervention group, a cost-saving (with improved health) is expected in the very short-term if there is a significant difference in duration of hospitalisation. Net savings will be estimated by comparing the length of stay with the costs of the intervention. The intervention cost, at a single primary recruiting site, will be assessed by prospective resource unit tracking including materials and time required for application/removal of eye-masks and noise protection. Resources will be costed using standard sources.

- Comparison of all health resource use to 2 years cPNA will be monitored prospectively to assess cost savings. Resource use will include hospital readmissions, general practitioner and specialist appointments, and any other health resources. Cost effectiveness will compare costs with measured clinical outcomes.
- Outcomes such as the Bayley-4 scores will provide surrogate information to undertake modelling to estimate long-term outcomes resulting from the intervention. Improvements in cognitive ability can translate to increased professional opportunities, and increased contribution to the wider economy. Economic evaluations will be consistent with established economic evaluation methods.⁵⁷

5.2 Study Design

The CIRCA DIEM trial is a multicentre, two-arm, parallel, Prospective, Randomised, Open, Blinded Endpoint (PROBE) controlled trial.

Very preterm infants are randomised to standard environmental care (control) or a cycled environment (light and noise) from birth until discharge. Participant flow charts are shown in

Figure 1 and Figure 2.

Figure 1 - Participant Flow Chart

cPNA – corrected postnatal age; ASQ – Ages and Stages Questionnaire; MPAS – Maternal Postnatal Attachment Scale; EPDS – Edinburgh Postnatal Depression Scale, GAD-7 – Generalised Anxiety Disorder Scale; ITSEA – Infant Toddler Social Emotional Assessment; CSBC-ITC - Communication and Symbolic Behaviour Scales Infant-Toddler Checklist; CESD-R - Center for Epidemiologic Studies Depression Scale Revised; ADOS-2 – The Toddler Module of the Autism Diagnostic Observation Schedule - Second Edition.

AN – antenatal; PNA – postnatal age; MPAS – Maternal Postnatal Attachment Scale; EPDS – Edinburgh Postnatal Depression Scale, GAD-7 – Generalised Anxiety Disorder Scale.

5.3 Minimisation of Bias

Infants meeting study eligibility criteria will be randomised to a control environment or a cycled environment (light and noise) from birth until discharge. Randomisation will use variable block sizes (block size 4 to 6) stratified by both gestation (<28 w, 28⁰-31⁶ w PMA) and study site, using the concealed randomisation facility built into the REDCap database via computer generated, randomisation tables developed and uploaded by the trial biostatistician ([name]) and maintained by the Trial Management Team at the Telethon Kids Institute. Randomisation will maintain equal group sizes between the two study arms. Infants from multiple pregnancies will be assigned to the same group, to ensure planned secondary analyses on parent mental well-being and attachment are not confounded by conflicting infant circadian rhythms.

Blinding of families, healthcare providers during initial hospitalisation, and the co-ordinating study investigators to group allocation is not possible for this intervention. However, outcome assessors and data analysts will be blinded to allocation.

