6.2.1 Informed consent

Parent/s or guardian of an eligible infant will be approached by a CIRCA DIEM trial researcher prior to birth or within the first 48 h postpartum. Informed parental consent to trial participation is required within the first 168 h (7 days) postpartum for the < 28 w infants and within the first 72 h postpartum for the ≥ 28 w infants. This is so that the trial intervention and data collection can be initiated as quickly as possible postpartum however recognising that the parents of <28 w infants require more time to reach a decision regarding the inclusion of their child in the trial and typically have a longer stay in NICU where the study intervention would be maintained for longer compared to the ≥ 28 w infants. Circumstances surrounding the condition of both the mother and child will first be taken into consideration in the timing of study information and consent.

The CIRCA DIEM researcher will provide the parent/s or guardian with trial information in the form of a brochure, information sheet, video, and consent form. Trial information which will be discussed in detail

with the parent/s or guardian, and all questions by the parent/s or guardian will be answered in full. Should the parents approve the enrolment of their infant, the mother or primary caregiver will be required to sign either the paper informed consent form or the electronic consent form sent via REDCap surveys allowing us to take the measurements and perform samples collections that are outlined in the study design information.

The primary carer/parent will also be requested to complete a section of the informed consent form for their participation in the mental well-being and maternal/infant assessments. They will also be asked for their permission to be contacted after the final study assessment in relation to future studies.

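### Small permuted blocks within site, with their sizes printed in the protocol of an open trial, let site staff guess the next allocation better than chance

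*Protocol*

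**What the plan says.** Protocol section 5.3 (Minimisation of Bias) sets out the scheme: "Randomisation will use variable block sizes (block size 4 to 6) stratified by both gestation" (below 28 weeks, and 28 to 31 weeks) "and study site, using the concealed randomisation facility built into the REDCap database via computer generated, randomisation tables". The trial biostatistician prepares and uploads the tables, which are then "maintained by the Trial Management Team at the Telethon Kids Institute". On the ratio it says: "Randomisation will maintain equal group sizes between the two study arms". Infants of one multiple pregnancy share an allocation.

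The same section says: "Blinding of families, healthcare providers during initial hospitalisation, and the co-ordinating study investigators to group allocation is not possible for this intervention". Protection is placed at the endpoint: "outcome assessors and data analysts will be blinded to allocation".

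On entry, section 6.2 makes parental consent an inclusion criterion, obtainable before or after birth. Section 6.2.1 says: "Informed parental consent to trial participation is required within the first 168 h (7 days) postpartum for the < 28 w infants"; the limit is 72 h at 28 weeks or more. Two exclusions in section 6.3 rest on judgement: critical illness with survival not expected, and being unlikely to return at 2 years.

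**The concern.** With two arms and equal allocation a block must be even, so a range of 4 to 6 allows only 4 and 6. Each site-by-gestation stratum has its own list. Site staff know the arms of the infants already enrolled in their unit, because the intervention cannot be hidden from them. Anyone who tracks these allocations can see which arm is behind and expect it to catch up. A concealed table does not prevent that.

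A guess matters only if it can be acted on. Here consent may follow birth by up to 3 or 7 days, and two exclusions call for judgement, so an enrolment can be pursued, timed or dropped. If guesses influenced which infants entered, the arms could differ in prognosis at entry. Blinded Bayley-4 assessment cannot undo that. The primary analysis in section 10.1 is an unadjusted t-test, so it would not correct such a difference either. The bias could run in either direction.

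**Working it through.** **Inputs.** Block sizes 4 and 6, stratification and 1:1 ratio: section 5.3. Total 954, 4-point target, SD 15 and 297 per group: section 10.2. Fourteen primary sites: section 6.1. Assumptions not in the protocol: the two sizes are equally likely, each allocation uses one slot, and the observer has the complete ordered log of the stratum.

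**The plan's own figure.** The protocol gives no predictability figure. Its sample size reproduces: a two-sample t-test for 4 points, SD 15, 5% two-sided and 90% power needs 297 per group (power 0.9005), and 600/0.7/0.9 = 952.4, taken to 954. It is used here only to size the strata: 954/(14 × 2) = 34 infants on average.

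**Hand check of the guess rate.** The simplest strategy is to guess the arm that is behind and toss a coin when the arms are level. The running difference returns to zero at every block boundary, so the observer needs neither the sizes nor the boundaries. In a block of 2m, the expected number of correct guesses is m + 2^(2m−1)/C(2m, m) − 1/2:

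- block of 4: 2 + 8/6 − 0.5 = 2.83
- block of 6: 3 + 32/20 − 0.5 = 4.10
- equal mix of 4 and 6: (2.83 + 4.10)/(4 + 6) = 69.3%

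This is the long-run rate; a list of 34 usually ends in an unfinished block, which lowers it slightly.

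**Simulation, lists of 34.** An observer who also knows the size set updates the probability of each block size and position after every allocation.

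| Block sizes | Best guess correct | Callable at ≥ 75% | Certain |
|---|---|---|---|
| 4, 6 | 68.9% | about 47% | about 6% |
| 6, 8, 10 | 65.7% | 26% | 1.7% |
| 6, 8, 10, 12 | 65% | 18% | 1% |

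For sizes 4 and 6, with lists of 17 to 68, the best guess is right 67.8% to 69.1% of the time, 44% to 49% of allocations are callable at ≥ 75%, and 5.5% to 5.8% are certain.

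**What publication adds.** Without the sizes, guessing the arm that is behind is right 68.8% of the time; with them, 68.9%. Disclosure therefore leaves the guess rate essentially unchanged and mainly supplies the certain cases, about 1 in 17.

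**What a guess could do to the primary comparison (illustration only).** Suppose recruiters shift expected prognosis by +h or −h Bayley points according to their guess, which is right with probability p. The difference between arms is then 2h(2p − 1). With p = 0.689 this is 0.756h. The standard error with 297 per group is 15 × √(2/297) = 1.23.

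| h (assumed) | Bias, points | Two-sided type I error |
|---|---|---|
| 0.5 | 0.38 | 6% |
| 1 | 0.76 | 9% |
| 2 | 1.51 | 23% |

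With p = 0.651 (sizes 6 to 12), the factor falls to 2 × 0.302 = 0.604h, about one fifth lower. Nothing in the protocol indicates the size of h, which may be zero.

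**The case against.** The case for leaving the scheme alone has several parts.

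- **Sizes vary, so few allocations are certain.** This stands: about 94% are not certain, and the finding is better-than-chance guessing, not knowledge.
- **The observer is idealised.** This stands as a reason to call the figures upper-end. Section 10.2 expects 30% multiple births, and how siblings use slots is not stated. Devices are worn at night, and section 7.2 also allows masks or ear-plugs around the clock for phototherapy or high-frequency ventilation. Still, staff who randomise infants learn each result and could keep a log.
- **The remedy is modest.** Mean guess accuracy falls only from 68.9% to about 65%, and the larger fall, from about 47% to 18%, depends on a chosen 75% cut-off. This is fair. The gain lies mainly in the allocations a recruiter would feel confident about.
- **There are safeguards.** Families are approached before birth or within 48 h (section 6.2.1), sites keep a register of potentially eligible infants (6.2), exclusion reasons are recorded (6.3), and clinicians are to be in equipoise (6.1). The secondary mixed model in section 10.1 adjusts for several prognostic factors. These may discourage or expose selection, but do not prevent it.

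Stronger readings are tempting, but the protocol does not support them. A reader might infer that holding the tables with the Trial Management Team lets sites predict allocations. It does not: the facility is described as concealed, and nothing gives sites access. Nor does the protocol show that this team is the same people as the unblinded co-ordinating investigators, or that the Biometrics team at the same institute would be a more independent custodian. A reader might also quote 31% certain allocations; that belongs to a fixed block of 4, which is not this design.

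**Conclusion.** The point holds in a limited form. Section 5.3 combines small blocks, site-level strata and open allocation, and prints the block sizes. An observer with a full stratum log could guess the next allocation correctly about 69% of the time, call about 47% at 75% probability or more, and be certain of about 6%. The result rests on equally likely sizes of 4 and 6, one slot per allocation and a complete log; stratum length matters little. The main driver is small blocks within site, not publication.

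This measures opportunity. It is not evidence that selection has occurred, and any effect on the Bayley-4 comparison depends on recruiter behaviour that the protocol cannot reveal. Severity is low to moderate: avoidable, cheap to reduce, and not fatal to the trial.

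**What to change.** 1. Remove the block sizes from section 5.3. State only that permuted blocks of varying size are used within strata, and keep the sizes in a restricted randomisation document. On its own this mainly removes the certain cases.
2. For strata still recruiting, load new lists for future allocations with a wider, undisclosed mix of block sizes, for example 6 to 12. This is the part that lowers the guess rate.

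The cost is a wording change and one upload of replacement lists. An unfinished block could leave a stratum unbalanced by up to 6 infants (half of 12) rather than 3 (half of 6), a small price against 954. No change of table custody is asked for here.
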